10.1.9 Biomarkers in Serum

10.1.9.1 GM-CSF and Anti-Drug Antibodies

Blood samples will be taken at the timepoints shown in *Table 1*.

At Baseline (Visit 2) and at Week 4 (Visit 3), samples for GM-CSF will be collected prior to dosing of trial drug. An additional sample for analysis of GM-CSF will be collected two hours after completion of trial drug administration at Baseline (Visit 2) and at Week 4 (Visit 3).

All samples for anti-drug antibodies will be collected prior to dosing at the appropriate clinic visit.

Analyses for GM-CSF and anti-drug antibodies (anti-GM-CSF, anti-Polyethylene glycol (anti-PEG) and anti-recombinant Human Albumin (anti-rHA)) antibodies will be performed using a GLP validated method.

10.1.9.2 Other Biomarkers

Blood samples will be taken at the timepoints shown in *Table 1*. The following biomarkers will be analysed: Krebs von den Lungen-6 (KL-6), Carcinoembryonic antigen (CEA), Surfactant Protein A (SP-A), Surfactant Protein B (SP-B), Surfactant Protein C (SP-C), Surfactant Protein D (SP-D), Cytokeratin Fragment 19 (Cyfra 21-1) and Lactate Dehydrogenase (LDH) after 4, 12, and 24-weeks treatment.

Analysis for these biomarkers will be performed by a central laboratory using validated methods. LDH will be analysed from the standard clinical chemistry sample.

10.2 Primary, Secondary, and Exploratory Endpoints

10.2.1 Primary Endpoint:

- Absolute change from baseline of (A-a)DO₂ after 24-weeks treatment.

At each visit, (A-a)DO₂ will be calculated centrally using the equation:

$$Aa \text{ Gradient} = \left(F_i O_2 (P_{atm} - P_{H_2O}) - \frac{P_a CO_2}{0.8} \right) - P_a O_2$$

where F_iO₂ is fraction of inspired oxygen

P_{atm} is ambient atmospheric pressure

P_{H₂O} is saturated vapour pressure of water at body temperature (set to 47 mmHg / 6.266 kPa)

P_aCO₂ is arterial partial pressure of carbon dioxide

P_aO₂ is arterial partial pressure of oxygen

10.2.2 Secondary Endpoints:

10.2.2.1 Key Secondary Endpoints

- Change from baseline in 6MWD after 24-weeks treatment
- Change from baseline in SGRQ total score after 24-weeks treatment
- Time to WLL during 24-weeks treatment
- Number of AEs, SAEs, ADRs, severe AEs and AEs leading to treatment discontinuation, including clinically significant changes in laboratory tests and electrocardiographic (ECG) variables, during 24-weeks treatment

10.2.2.2 Further Secondary Endpoints:

- Absolute change from baseline in VC (% predicted), DLCO (% predicted), FEV₁ (% predicted) and FVC (% predicted), and relative change from baseline in PaO₂ after 24-weeks treatment
- Number of subjects with >5 mmHg/>0.67 kPa and number of subjects with >10 mmHg/>1.33 kPa improvement in (A-a)DO₂ after 24-weeks treatment
- Number of subjects with >5 percentage points and number of subjects with >10 percentage points improvement in VC (% predicted) after 24-weeks treatment
- Number of subjects with >10 percentage points improvement in DLCO (% predicted) after 24-weeks treatment
- Number of subjects with >10 percentage points improvement in FEV₁ (% predicted), FVC (% predicted) after 24-weeks treatment
- Number of subjects with >10% relative improvement in PaO₂ after 24-weeks treatment
- Number of subjects with improved tolerance to exercise (increase in distance walked ≥50 m or desaturation <4 percentage points on the 6MWT) after 24-weeks treatment
- Change from baseline in dyspnoea score and cough scores after 24-weeks treatment

- Number of subjects with improved CT score after 24-weeks treatment

10.2.3 Exploratory Endpoints

10.2.3.1 Double-Blind Treatment Period

- Absolute change from baseline of (A-a)DO₂, VC (% predicted), DLCO (% predicted), FEV₁ (% predicted), FVC (% predicted), and relative change from baseline of PaO₂ after 4 and 12-weeks, treatment
- Time period during which the (A-a)DO₂ level is maintained below Baseline –10mmHg
- Number of subjects with improved tolerance to exercise (increase in distance walked ≥ 50 m or desaturation <4 percentage points on the 6MWT) after 4 and 12-weeks treatment
- Time period during which the improvement in tolerance to exercise is maintained
- Change from baseline in dyspnoea score and cough scores after 4 and 12-weeks treatment
- Number of subjects with improved QoL (change of ≥4 units on the SGRQ/number of subjects with 'no problems' in the EQ-5D-5L), after 4, 12, and 24-weeks treatment
- Change in serum concentration of biomarkers; KL-6, CEA, SP-A, SP-B, SP-C, SP-D, Cyfra 21-1 and LDH after 4, 12, and 24-weeks treatment
- Levels of anti-GM-CSF after 4, 12 and 24-weeks treatment
- Change in serum concentration of GM-CSF post first dose of trial drug and after 4-weeks treatment
- Number of subjects in need for oxygen supplement therapy during 24-weeks treatment
- The distribution of DSS at Screening and at Week 24
- The percentage of subjects with DSS 1 or 2 at Week 24

10.2.3.2 Follow-up period

- Number of subjects requiring WLL, or other treatment for aPAP and number of treatment courses required during 24-weeks or 48-weeks follow-up
- Time to WLL, or other treatment for aPAP during 24-weeks or 48-weeks follow-up
- Absolute change from baseline in (A-a)DO₂ and VC (% predicted), DLCO (% predicted), FEV₁ (% predicted), and FVC (% predicted), and relative change from baseline of PaO₂ after 12, 24, 36 and 48-weeks follow-up
- Number of subjects with improved tolerance to exercise (increase in distance walked ≥50 m or desaturation <4 percentage points on the 6MWT) after 12, 24, 36 and 48-weeks follow-up
- Number of AEs, severe AEs, SAEs and ADRs, including clinically significant changes in laboratory tests and ECG variables, during 24-weeks or 48-weeks follow-up
- Levels of anti-GM-CSF after 12 and 24 weeks follow-up
- The distribution of DSS after 24 and 48-weeks follow-up
- The percentage of subjects with DSS 1 or 2 after 24 and 48-weeks follow-up

10.3 Demographic and Other Baseline Characteristics

10.3.1 Demographic and Baseline Data

The following demographic and baseline data will be collected at Screening (Visit 1):

- Date of birth
- Weight and height
- Sex
- Race (White/Asian/Black/American Indian or Alaska Native/Native Hawaiian or Other Pacific Islander, according to FDA)
- Date of aPAP diagnosis
- Smoking (Previous/Current/Never)
- Previous exposure to GM-CSF (Yes/No) (Administration within three months of Baseline is an Exclusion criterion, *Section 8.3*)
- Previous WLLs (Total number, date for last WLL) (WLL within one month of Baseline is an Exclusion criterion, *Section 8.3*)

10.3.2 Medical History

Medical history will be recorded at Screening (Visit 1).

10.3.3 Recording of Prior and Concomitant Medication/Therapy

Prior and concomitant therapies allowed during the trial are detailed in *Section 9.4*.

Prior medication/therapy is defined as medication/therapy administered prior to first dose of trial medication. All medication/therapy administered after first dose of trial medication is considered concomitant medication/therapy.

At Baseline (Visit 2) prior medications/therapies administered within three months will be recorded. In the Double-blind treatment period at Weeks 4, 8, 12, 16, 20 and 24 (Visits 3, 4, 5, 6, 7 and 8) concomitant medication/therapy administered from first dose of Double-blind treatment given will be recorded.

In the Follow-up period at 4, 12, 24 and 48 weeks after the end of the Double-blind treatment period (4-week FU, 12-week FU, 24-week FU and 48-week FU Visits) only concomitant medications and treatments outlined in *Section 9.4* will be recorded.

The following information will be collected and recorded on the concomitant medication/therapy page of the eCRF throughout the trial for prior and concomitant medications: Drug name (product name), route, dose and units, frequency, indication, reference to AE if applicable, start date, end date or ongoing at the end of the trial will be recorded. Prior and concomitant medications will be coded using World Health Organisation (WHO) Drug Dictionary.

10.3.3.1 Whole Lung Lavage

WLL is applied as rescue therapy during the trial. The criterion for performing WLL is clinical worsening of aPAP based on symptoms, reduced exercise capacity and/or findings of hypoxemia or desaturation according to the Investigator's judgement. The reason(s) for conducting WLL should be documented. The date, when this criterion applies and thus an indication for WLL is present, will be recorded in the CRF.

The following information will be collected and recorded on the concomitant medication/therapy page of the eCRF throughout the trial for prior and concomitant WLL procedures: Date, start and end time, type of WLL, saline volume. Anesthesia drugs should be recorded as concomitant medication(s).

10.3.3.2 Oxygen Supplementation

Oxygen supplementation will be collected and recorded on the concomitant medication/therapy page of the eCRF throughout the trial for prior and concomitant supplementation.

Oxygen supplementation given only during assessments (according to *Section 10.1.1 or 10.1.3*) will not be recorded on the concomitant medication/therapy page, but under lung function and 6MWT pages, respectively.

10.4 Safety Assessments

10.4.1 Safety Variables

The following safety variables will be assessed:

- AEs
- Physical examination
- Vital signs
- Laboratory safety assessments
- HR-CT

10.4.2 Adverse Events

Any AEs will be reported during the trial period from Baseline (Visit 2) to the completion of the 24- week or 48-week Follow-up visits (Visit 11 and 13). The subjects will be encouraged to contact the clinic in between visits if they experience AEs or have any concerns. For further information of definitions and reporting of AEs and SAEs, see *Section 11*.

A Diary Card will be given to the subject at start of treatment at the Baseline Visit (Visit 2) and at Weeks 4, 8, 12, 16 and 20 (Visits 3, 4, 5, 6 and 7) at Weeks 12, 24 and 36 of the Follow-up period (Visits 10,11 and 12). In the Diary Card the subject will record any AEs and answer specific questions regarding potential pulmonary and systemic effects. The completed Diary Card will be collected at the next clinic visit (Visits 3, 4, 5, 6, 7, 8, 10, 11, 12 and 13). At these visits, the investigator will evaluate the safety information on the Diary Card and record any AEs on the eCRF.

10.4.3 Physical Examination

All subjects will undergo a standard physical examination at the timepoints shown in *Table 1*. Any abnormalities will be recorded in the eCRF.

10.4.4 Vital Signs

The following vital signs will be assessed at the timepoints shown in *Table 1*.

- Resting systolic and diastolic blood pressure (mmHg), after 5 minutes sitting
- Resting heart rate (beats per minute), after 5 minutes sitting
- Resting respiration rate (breaths per minute), after 5 minutes sitting

- Oral body temperature (°C)

The observed values will be recorded and assessed as 'normal' or 'abnormal'. Abnormal findings will be assessed as 'clinically significant' or 'not clinically significant'.

10.4.5 Electrocardiogram

A 12-lead ECG will be assessed using a standard ECG machine according to local procedures at the time points shown in *Table 1*. Heart rate, QRS, PR and QT intervals will be recorded from the ECGs. The ECGs will be interpreted and signed and dated by the investigator or his/her designee. Results will be classified as normal, having a non-clinically significant abnormality, or having a clinically significant abnormality. All clinically significant abnormalities will be recorded as AEs.

10.4.6 Laboratory Safety Assessments

The laboratory safety analyses (haematology and clinical chemistry) will be performed by a central laboratory at the timepoints shown in *Table 1*. Sampling methods and procedures will be in accordance with local routine care.

The following laboratory safety parameters will be analysed:

Table 2 Laboratory Safety Parameters

Category	Laboratory Parameter
Haematology	Haemoglobin, Red Blood Cell Count (RBC), Red Blood Cell Distribution Width (RDW), Haematocrit (PCV/EVF), Mean cell volume (MCV), Mean cell haemoglobin (MCH), Mean cell haemoglobin concentration (MCHC), Platelet count, White cell count, and white cell differential absolute and percentage count: Neutrophils, Lymphocytes, Monocytes, Eosinophils, Basophils, Prothrombin Time International Normalised Ratio (PT-INR)
Clinical Chemistry	Aspartate Aminotransferase (AST), Alanine Aminotransferase (ALT), Gamma Glutamyl Transpeptidase (GGT), Alkaline Phosphatase, Bilirubin,, Urea, S-Creatinine, Potassium, Sodium, Calcium, Chloride, Phosphate, Total protein, Albumin, LDH*, C-Reactive Protein (CRP), and Glucose (non-fasting)

* LDH will be analysed as a biomarker

The observed values will be recorded and assessed as 'normal' or 'abnormal'. Abnormal findings will be assessed as 'clinically significant' or 'not clinically significant'.

10.5 Pregnancy Test

A serum pregnancy test will be performed for female subjects at Screening (Visit 1), at dosing at Baseline (Visit 2) and at all subsequent visits during the Double-blind and Follow-up treatment period. A urine pregnancy test will also be performed before dosing at Baseline (Visit 2) in order to **immediately** confirm that the subject is not pregnant.

10.6 Appropriateness of Measurements

Standardised methods for measurements of efficacy and safety variables will be used.

10.7 Handling of Laboratory Samples and Total Blood Volume

A trial specific laboratory manual for sampling, handling, storage and shipment of samples will be provided to the site personnel. The manual will be provided to the site before start of the trial.

Blood samples for efficacy and safety assessments will be taken at all visits, except for Visit 9, which is a telephone follow-up. For the Double-blind period of 24 weeks the amount of blood required per patient per visit varies between 10 mL and 53 mL pr. visit. The total amount needed for the Double-blind period is approximately 250 mL. For the Follow-up period of 24 or 48 weeks the total amount of blood required per patient is approximately 85 mL, with a maximum of 26.2 mL for one visit.

11 SAFETY

11.1 Definitions

11.1.1 Adverse Event

Any untoward medical occurrence in a patient or clinical trial subject administered a medicinal product and which does not necessarily have a causal relationship with this treatment.

Comment: An AE can therefore be any unfavourable and unintended sign (including an abnormal laboratory finding), symptom, or disease temporally associated with the use of an IMP, whether or not considered related to the IMP.

11.1.2 Adverse Drug Reaction

All untoward and unintended responses to an IMP related to any dose administered.

Comment: All AEs judged by either the reporting investigator or the sponsor as having a reasonable causal relationship to a medicinal product qualify as adverse drug reactions. The expression reasonable causal relationship means that a causal relationship between a medicinal product and an AE is at least a reasonable possibility i.e. the relationship cannot be ruled out.

11.1.3 Unexpected Adverse Reaction

An adverse reaction, the nature or severity of which is not consistent with the applicable product information (e.g. IB for an unauthorised IMP or summary of product characteristics for an authorised product).

Comment: When the outcome of the adverse reaction is not consistent with the applicable product information this adverse reaction should be considered as unexpected.

11.1.4 Serious Adverse Event

Any untoward medicinal occurrence or effect that at any dose:

- Results in death
- Is life-threatening
- Requires hospitalisation or prolongation of existing hospitalisation
- Results in persistent or significant disability or incapacity
- Is a congenital anomaly or birth defect
- May jeopardise the subject or may require intervention to prevent one or more of the other outcomes listed above (Important Medical Events)

Comments: Life-threatening in the definition of a SAE or serious adverse reaction refers to an event in which the subject was at risk of death at the time of event; it does not refer to an event which hypothetically might have caused death if it was more severe.

For important medical events, medical judgement should be exercised in deciding whether an AE/reaction is serious.

The severity of an adverse reaction is largely determined by the outcome of the medical occurrence. An adverse reaction should only be termed "serious" if hospitalisation did in fact take place as a result of it. As a rule, hospitalisation is the admission to a hospital with at least one overnight stay.

The presentation of a patient in the emergency room (casualty center, health care center) alone without subsequent in-patient admission does not yet fulfill the criterion hospitalisation. However, it should be confirmed whether any of the other criteria mentioned above justifies an adverse reaction being classified as "serious" or at least "medically significant."

If the Investigator becomes aware of an SAE with a reasonable relationship to the IMP after the subject has left the trial, this SAE must also be reported (post-trial event).

11.2 Suspected Unexpected Serious Adverse Reaction (SUSAR)

A SUSAR is an AE which

- has a reasonable possibility of causal relationship to an IMP,
- is serious; and
- is unexpected

Therefore, due to the nature and/or severity of the adverse reaction, a SUSAR is not consistent with the applicable product information (i.e. the reference safety information in the IB) for the IMP used in this study.

11.3 Reporting of Adverse Events

All trial subjects will be carefully monitored for the occurrence of AEs during the trial period from Screening (Visit 1) to the completion of the 48-week Follow-up visit (Visit 13). The investigator will collect AEs with a non-leading question such as "have you experienced any new health problems or worsening of existing conditions" as well as reporting events directly observed or spontaneously volunteered by subjects.

Clearly related signs, symptoms and abnormal diagnostic procedure results should be grouped together and reported as a single diagnosis or syndrome whenever possible.

All AEs including but not limited to events reported by the subject, or reported in answer to an open question by the investigator or member of this team, which fall into any of the above definitions must be recorded as an AE in the eCRF and should include the following information:

- Brief description of the event (diagnosis)
- Start date (and time, if relevant)
- Stop date (and time, if relevant) (or resolution)
- Severity
- Action taken regarding trial drug
- Opinion on causality
- Seriousness

Outcome

Severity

Severity describes the intensity of an event, and will be assessed as:

Mild

The AE is easily tolerated and does not interfere with daily activity.

Moderate

The AE interferes with daily activity, but the subject is still able to function. Medical intervention may be considered.

Severe

The AE is incapacitating and requires medical intervention.

If an AE changes in severity, it should be reported as an AE of new severity but with the same description.

Causality

Causality will be assessed as:

Probable

A clinical event, including laboratory test abnormality, with a reasonable time sequence to administration of the IMP, unlikely to be attributed to concurrent disease or other drugs or chemicals, and which follows a clinically reasonable response on withdrawal (dechallenge). Rechallenge information is not required to fulfil this definition.

Possible

A clinical event, including laboratory test abnormality, with a reasonable time sequence to administration of the IMP, but which could also be explained by concurrent disease or other drugs or chemicals. Information on IMP withdrawal may be lacking or unclear.

Unlikely

A clinical event, including laboratory test abnormality, with a temporal relationship to IMP administration which makes a causal relationship improbable, and in which other drugs, chemicals or underlying disease provide plausible explanations.

Not applicable

This assessment can be used e.g. in cases where the subject did not receive any treatment with IMP or if the causality cannot be judged because information is insufficient or contradictory.

Outcome

The outcome of AEs has to be described by following criteria:

- Recovered
- Not Recovered
- Recovered with sequelae
- Fatal
- Unknown.

Follow-up of Subjects after Adverse Events

Any AE that is ongoing when the subject is withdrawn from the trial should be followed-up until the AE is resolved or the investigator decides that the AE is stable and needs no further Follow-up.

Abnormal Laboratory Values/Vital Signs

An asymptomatic abnormal laboratory/vital sign finding should only be reported as an AE if it is clinically significant according to the investigator's assessment, if it fulfils the criteria for an SAE or if it causes the subject to discontinue the trial.

If an abnormal laboratory/vital sign value is associated with clinical signs and symptoms, the sign/symptom should be reported as an AE and the associated laboratory/vital sign result should be considered additional information.

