5.3.11 Adverse Events

AEs will be coded according to the Medical Dictionary for Regulatory Activities (MedDRA) system and tabulated by System Organ Class (SOC) and by Preferred Term (PT).

A summary table will be presented with No. of subjects with AEs, No. of subjects with serious AEs, No. of subjects with severe AEs, No. of subjects with ADRs (probable or possible), Number of subjects with at least one AE leading to discontinuation, and also the number of AEs, severe AEs, serious AEs, ADRs (where a certain AE is only counted once within each subject on a preferred term level).

The total number of subjects with at least one AE and the number of AEs will be derived and summarised by SOC and PT.

Similar tables will be created for serious adverse events.

AEs will also be tabulated by severity (mild, moderate and severe) and relationship to treatment (probable, possible, unlikely or not applicable). Adverse events occurring or worsening after first treatment will be included in summary tables. Any AEs reported before first treatment will only be included in listings.

In listings of AEs the relative day counted from first administration of IMP (Day 1) will be presented together with the relative day from the latest administration of IMP (the actual dates will also be included).

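### Two safety-classification texts conflict with the protocol's own definitions and can under-classify events: unassessable causality drops out of the ADR count, and one sentence ties 'serious' to hospitalisation alone

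*Protocol*

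**What the plan says.** **Causality.** Protocol 11.1.2 counts an AE as an ADR when "a causal relationship between a medicinal product and an AE is at least a reasonable possibility i.e. the relationship cannot be ruled out". One party's view is enough: the event need only be "judged by either the reporting investigator or the sponsor as having a reasonable causal relationship to a medicinal product". The causality scale in protocol 11.3 has four levels: probable, possible, unlikely and not applicable. The last may be used, for example, when the subject took no IMP, "or if the causality cannot be judged because information is insufficient or contradictory".

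SAP 5.3.11 plans a summary table with "No. of subjects with ADRs (probable or possible" as its ADR line. It also tabulates AEs by "relationship to treatment (probable, possible, unlikely or not applicable". Protocol 10.2.2.1 lists the numbers of ADRs and SAEs within a key secondary endpoint.

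**Seriousness.** Protocol 11.1.4 gives six alternative criteria: death, threat to life, hospitalisation or its prolongation, disability, congenital anomaly, and important medical event. A later comment says that a reaction should be called serious only "if hospitalisation did in fact take place as a result of it". The paragraph after that says that an emergency-room visit without admission does not meet the hospitalisation criterion, but that the other criteria should be checked.

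**Reporting.** Protocol 11.2 defines a SUSAR as an event that is serious, unexpected and "has a reasonable possibility of causal relationship to an IMP". Protocol 11.4 requires all SAEs to be reported within 24 hours of awareness, from consent to Day 30 after the last visit. After that, only serious events related to study medication must be reported.

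**The concern.** The ADR definition sets a low threshold: anything not ruled out is in. The coding scale and the SAP together set a higher one: somebody must have judged the event at least possible. Events for which nobody could form a judgement fall between the two. They share a code with subjects who never took the product, and the SAP leaves that code out of the ADR line.

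The hospitalisation sentence has the same direction. It applies to adverse reactions, which are the events from which SUSARs are drawn, and taken literally it removes five of the six criteria for them.

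At stake is whether a reported safety count matches its own definition, in what protocol 5.1 calls this sponsor's first trial of the product in PAP patients. Where serious reactions are few, the classification of a single event can matter. No efficacy test is involved: SAP 5.4 confines the multiplicity procedure to the primary endpoint and the three key secondary efficacy endpoints.

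**Working it through.** The documents give no rate of unassessable causality and no rate of serious reactions without admission, so there is no figure to reproduce. The check is a comparison of texts.

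**A. Causality**

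1. Condition for an ADR (protocol 11.1.2): the relationship cannot be ruled out.
2. Condition for Not applicable in a dosed subject (protocol 11.3): information too thin or too conflicting to judge causality. Information that does not support a judgement does not support an exclusion either, so such an event meets condition 1.
3. Counting rule (SAP 5.3.11): ADR = probable or possible. Not applicable is outside the count.
4. Who is in the tables: SAP section 4 bases safety summaries on DB-SAF (at least one dose), and SAP 5.3.11 limits summary tables to events arising or worsening after first treatment. The no-IMP use of the code therefore cannot occur there. What remains in the Not applicable column is chiefly unassessable events (chiefly, because 11.3 offers its two cases as examples).
5. When the code is likely to be used: protocol 11.4 makes causality a mandatory field of the initial SAE report, which is due within 24 hours even if data are incomplete. Sections 11.3 and 11.4 ask for follow-up reports, but neither says that a Not applicable entry must later be replaced.
6. Sponsor judgement: it can make an event an ADR under 11.1.2, but SAP 5.3.11 does not say how it enters the count.

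Size: let *A* be the probable or possible events and *U* the unassessable events after first dose. The SAP reports *A*; the definition gives *A* + *U*. The relative shortfall is *U* / (*A* + *U*). Neither term is given. With *U* = 0 the shortfall is 0.

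**B. How far the causality code reaches**

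- SAE count during the trial: reporting under 11.4 does not depend on causality, so it is unaffected.
- SUSARs during the trial: the test in 11.2 is not tied to the investigator's code, the sponsor's view counts (11.1.2), and the pharmacovigilance vendor assesses SAEs (11.10). A miss is possible but not implied.
- After Day 30 following the last visit: the duty in 11.4 covers only related serious events, on the investigator's assessment. An unassessable serious event then has no stated reporting duty. Exposure is larger here.

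**C. Seriousness (protocol 11.1.4)**

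| Reaction | Six-criterion list | Hospitalisation sentence | Emergency-room paragraph |
|---|---|---|---|
| Overnight admission | serious | serious | not needed |
| Life-threatening, treated in the emergency room, discharged | serious | not serious | other criteria to be checked, so can be serious |
| Fatal at home, no admission | serious | not serious | not addressed |
| Important medical event, no emergency-room or health-centre visit | serious on medical judgement | not serious | not addressed |

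The list and the sentence agree only in the first row. The repairing paragraph reaches only the second. It also offers a medically significant label as a fallback, although the list already makes important medical events serious.

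**The case against.** The case against is substantial, and much of it stands.

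- *The code is optional and overlaps with Possible.* Protocol 11.3 permits Not applicable; it does not require it. Possible already covers events with a reasonable time sequence and other explanations, even if withdrawal information is missing. Many thin-information events will be coded there. This stands and makes the affected number smaller; it does not remove the conflict for events that are coded Not applicable.
- *Nothing disappears.* All four categories are tabulated, so a reader can find the events. This stands, but the ADR line itself still departs from its definition.
- *Seriousness is handled by context.* The next paragraph of 11.1.4 asks for the other criteria to be checked, and 11.4 makes seriousness criteria a mandatory report field. The sentence is probably a badly drafted note on hospitalisation. This largely stands for emergency-room cases. It does not cover other reactions without admission, and the reporting and assessment steps in 11.4 and 11.10 start only once the site has called an event serious.
- *Equal treatment of arms.* Investigators code blind and the rule is the same in every arm. This stands: the documents show no bias between arms.

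A reader might infer more than this. That Not applicable lowers the SAE count is wrong, because in-trial SAE reporting ignores causality. That an unexplained death would escape SUSAR reporting is not shown: death is itself a seriousness criterion, and the sponsor's judgement and the vendor's assessment also apply. That the DSMB sees filtered data has no support: no section says that its listings depend on these codes, and its charter is not among the documents. The Safety Management Plan and the trial-specific SAE procedure, also not available, may settle some of this.

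**Conclusion.** Both inconsistencies are in the text and should be corrected. Applied as written, protocol 11.3 with SAP 5.3.11 can give an ADR count below the one that protocol 11.1.2 defines, and the hospitalisation sentence in 11.1.4 contradicts the list above it. Both texts err towards fewer events classified as drug-related or serious.

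The size is unknown and could be zero. Any percentage would rest on assumed coding rates, so none is offered. The firm consequence is limited to the ADR count. A missed SUSAR is a risk, greater after Day 30 following the last visit, and under-classification of seriousness is a risk mainly for reactions outside the emergency-room case. Efficacy conclusions are untouched.

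The causality point rests on one assumption: that an event whose causality cannot be judged has not been ruled out. The protocol's own gloss on reasonable possibility supports this. A reader might extend the argument to Unlikely, which 11.3 describes as improbable, not as excluded. That case is weaker, because there an assessor has reached a judgement against causality; the wording could be clarified at the same time.

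**What to change.** 1. Protocol 11.3: restrict Not applicable to subjects who received no IMP. State that causality which cannot be assessed after first dose is handled as not ruled out, that is as related, until further information resolves it.
2. SAP 5.3.11: count AEs in DB-SAF with unassessable causality as ADRs, or show the ADR count both ways. State how a sponsor judgement of relatedness enters the count.
3. Protocol 11.1.4: reword the sentence so that it says only when the hospitalisation criterion is met, leaving the other five criteria intact.

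Cost: protocol and SAP wording and a note on eCRF completion. The ADR count may be slightly higher, and there may be a few more expedited reports. No efficacy analysis and no sample size changes.
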